1. SYNOPSIS

Title	A Lead-in Study Evaluating Efficacy of GuessWhat Mobile App Therapy for Children With Autism
Design	Randomized, Investigator-Blinded,
Objectives	Determine whether GuessWhat Dtx can improve socialization in children with ASD after 4 weeks of use.
Endpoints	Primary: Change from week 0 to week 4 in the Vineland Adaptive Behavior Scales-3 Socialization Subscale, Comprehensive Parent Report Secondary: Change from week 0 to week 4 in Parent Stress Scale, and Child Emotion Recognition Score Exploratory/Descriptive: Descriptive analysis of child/parent surveys, treatment regimen compliance, demographics, missing data, and any resulting treatment related AEs
Study Sites	Participants will recruited by Stanford via remote online recruitment.
Planned Enrollment	A minimum of 500 to a maximum of 2,000 participants will be enrolled to achieve a minimum of 360 to a maximum 900 completed participants (n=180 - 450 in each of 2 arms) evaluable
Study Population	Autistic children 3-12 years old.
Subject Entry Criteria	Inclusion Criteria (1) Parent who is at least 18 years old of child with autism. (2) Child with autism is between 3 and 12 years old at time of baseline data collection. Exclusion Criteria (1) Parent does not have an Android or iOS smartphone compatible with GuessWhat App. (2) The parent is unable to speak/read in available translations of the study app: English, Spanish, Brazilian Portuguese.
Randomization	Block randomization stratified by child sex.
Treatment Regimen (Standard dose)	App is used 3 times a week for 15 minutes for 4 weeks

Duration of Study Participation	8 weeks
Statistical Methods	Independent Samples T-Tests
Study Measurements: Efficacy, Safety	Efficacy: Change in Vineland Adaptive Behavior Scales-3 Socialization Subscale week 0 to week 4 Safety: Adverse event reporting

3. INTRODUCTION

3.1 Background Information

We have built a prototype mobile app (guesswhat.stanford.edu) that engages children in a fluid social interaction with a social partner (e.g. mom or dad), turning the focus of the camera on the child and reinforcing prosocial learning while simultaneously measuring the child's progress in socialization. Our pilot statistics demonstrate that our development efforts are making the application more popular and engaging, with the 28-day active user base currently at over 500 users (~80% of whom are on iOS as the leading version of the app and average 4-week retention up to 25% and climbing too, respectively. To date, the app has generated more than 16,000 game sessions yielding 3,000+ videos (75+ hours) and more than 2 million highly emotive frames

that demonstrate the app's potency for data acquisition. This early success supports the prediction that GW will generate enough data to build computer vision algorithms that can automatically classify key features including, but not limited to, emotion, eye gaze, and gestures. In addition to the potential for AI model development is GW's potential for therapeutic intervention.

3.2 Previous studies

We examined the therapeutic feasibility of GuessWhat in 72 children (75% male, average age 8 years 2 months) with autism who were asked to play the game for three 90- second sessions per day, 3 days per week, for a total of 4 weeks. The group showed significant improvements in Social Responsiveness Score-2 (SRS-2) total (3.97, $p < .001$) and Vineland Adaptive Behavior Scales-II (VABS-II) socialization standard (5.27, $p=0.002$) scores.

These results demonstrated clinically significant improvements consistent with or better than previously reported behavioral therapy intervention outcomes in similarly aged participants. Overall, families played an average of 18 90-second game sessions over the four weeks, with an average of three 90-second gameplay sessions per day of use and average of six days of use over the four weeks. These sessions generated almost 1,000 videos (24 hours in total) used to generate 300,000+ frames labeled with a host of app and sensor data such as choice of game deck, number of correct guesses, etc., providing strong evidence for the feasibility of using GW to generate a rich behavioral database for training pediatric neurodevelopmental AI models.

3.3 Rationale for the Current Study

While multiple studies have demonstrated that the delivery of behavioral therapy as early as possible can effectively treat and even eliminate an ASD diagnosis,^{9–13} wait times to receive a diagnostic evaluation can,¹⁴ exceed 14 months,¹⁵ and out-of-pocket expenses can reach \$80,000 per year¹⁶ leaving one in three autistic children in the United States unable to receive the standard care. Geographic isolation and coronavirus disease 2019 (COVID-19) related lockdowns present further limitations in access to consistent and adequate treatment.

We previously demonstrated that wearable augmented reality glasses such as Superpower Glass, can deliver significant therapeutic benefits to children with autism using a fun exchange between the autistic child and a caregiver through games such as “Capture The Smile” where the child must get the caregiver to express a series of emotions. Other mobile interventions, such as AKL-T01 (EndeavorRx, Akili Interactive Labs, San Francisco, California, United States), the first game-based therapeutic to receive market clearance by the FDA in June 2020, have shown therapeutic effectiveness in attention deficit/hyperactivity disorder (ADHD), anxiety, depression, and other mental health conditions. This growing body of evidence highlights the potential for scalable digital therapies to provide access to care to patient populations in the United States and globally.

4. DESIGN

4.1 Study Design

This is a Phase 2 randomized design. The intervention period is 4 weeks. Total study length is 8 weeks. Outcomes assessors will not be blinded, but the investigator will be blinded.

4.2 Study Sites

We will recruit remotely via email marketing.

Requirements for site selection and site registration: Sites will be evaluated by Stanford team and the main PI prior to selection or activation.

Recruitment and enrollment will be decentralized and handled by a single study coordinator located at Stanford.

We will enter into formal collaboration/DUA agreements with sites who wish to be involved in the study/have access to the study data.

We will evaluate potential study sites by

1/Patient population and demographics: are there patients who meet study criteria who will be willing/able to participate?

2/ Is the study site willing to post promotional materials on site and support communication via initial recruitment email/contact?

5. OBJECTIVES

5.1 Primary Objective

To evaluate the effects of a social game-based digital therapeutic, GuessWhat, on adaptive socialization when used consistently over 4 weeks in children with autism 3-12 years compared to a waitlist control group.

5.2 Secondary Objectives

To see if use of a social game-based digital therapeutic can lead to changes in emotion recognition and parent stress when used consistently over 4 weeks.

To understand whether there is a difference in clinically meaningful changes if the device is used 4 weeks continuously.

To understand what demographic variables (if any) make patients more likely to respond to the treatment.

To understand the safety of device when used at home with a parent/caregiver.

6. SUBJECT POPULATION

6.1 Inclusion Criteria

(1) Parent who is at least 18 years old of child with autism.

(2) Child with autism is between 3 and 12 years old at time of baseline data collection.

6.2 Exclusion Criteria

(1) Parent does not have an Android or iOS smartphone compatible with GuessWhat App.

(2) The parent is unable to speak/read in available translations of the study app: English, Spanish, Brazilian Portuguese.

(3) We will exclude participants who have a self-reported concurrent psychiatric or neurologic diagnosis including genetic syndromes and epilepsy.

6.3 Removal of Subjects from Treatment

We will remove subjects from treatment if they experience any negative effects. We will also remove subjects from treatment if there is suspicion of fraudulent activity (i.e. impersonating a parent of child, etc.)

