7.2 Administration of GuessWhat

We will include several screening steps prior to enrollment. These will include: (1) completion of a short screening questionnaire, (2) Completion of baseline measures online, Demographics age matches baseline DOB, Time to complete baseline >20 minutes (not required, but will be flagged if not met), Missing data <40% (not required, but will be flagged if not met), Commitment task where a parent is asked to upload a picture of their child participating and confirm they understand participant responsibilities.

A coordinator will complete the above screening steps, and if the participant meets all requirements, will randomize the participant. Treamtent participants will receive a link to download the app.

GuessWhat is administered by the parent initiating play with the child. The parent interacts with the child throughout gameplay to administer the treatment for the recommended dose.

The current trial's control is a treatment as usual group. Control participants will be asked to continue their treatment, and to inform the study team of any changes in treatment regimen during follow up assessments.

Treatment Compliance

After randomization and enrollment, research coordinators will monitor activity and contact participants by phone or email if there is no activity within the first 7 days. Participants will receive 3 reminders before being marked as lost to follow-up. The app will also send automatic notifications and automated email reminders will be sent weekly to remind parents to engage with the app.

Treatment Precautions

We identified no critical tasks during our use related risk analysis. We used simulated use to identify user tasks and determine associated hazards. To date No Adverse Events have been reported through testing. Following completion of Clinical Trial, we will include all adverse event information. We determined that use of the app presents no greater risk than a child and parent encounters in daily life.

Concomitant Therapy

We will not prohibit any concomitant therapy, pharmaceutical or behavioral. We will collect information on concomitant therapy and treatment at week 4, 8, 12.

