8.1 Screening and Enrollment Steps

Week 0/Screening and Baseline Assessment

Participants will be screened, consented, and enrolled entirely online using electronic data capture. Parents/Guardians and coordinators will complete the following steps prior to enrollment via online forms:

- Screening questionnaire completed online
- Informed Consent administered and obtained online (waiver of documentation approved)
- Baseline questionnaires completed (Demographics, Mobile Autism Risk Assessment (MARA), Parent Stress Scale, VABS-3 Socialization subscale parent report, Emotion Recognition Child online Task
- review of baseline data completed by coordinator

Week 1: Enrollment and Allocation

- Upon receiving notification with download link and download access code, participant downloads the app and is automatically randomized to treatment or control using a pre-defined block randomization scheme developed by the statistician.

[Weeks 1-4: Intervention](#)

If randomized to Control, participants will continue treatment as usual. When they log-in to the app, they will receive a message that they will wait a few more weeks before beginning treatment.

If randomized to Treatment, participants will be asked to play the app 3 times a week for 10-15 minutes for the next 4 weeks and they will receive weekly push notifications and email reminders.

[Week 4 Post-Test 1](#)

Treatment and Control will be asked to complete all outcome measures and will be asked about any changes in treatment or safety events at week 4. Participants will also be asked to complete a question assessing time spent playing with their child over the last month in emotion-centric theatrical play.

[Week 8 Post-test 2](#)

At week 4 from initial app download date, participants will be asked via email to complete all outcome measures as well as check-in on any changes in treatment and any safety events. These will be collected via RedCap online surveys.

[Week 12 Post-test 3 Follow-Up](#)

Treatment and Control will be asked to complete all outcome measures and will be asked about any changes in treatment or safety events at week 4. Participants will also be asked to complete a question assessing time spent playing with their child over the last month in emotion-centric theatrical play.

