10.2 Sample Size Justification and Power Calculation

We will enroll up to 2,000 participants to achieve a 50% enrollment rate and 36% retention rate.

We aim to successfully retain 36% of enrolled families and have 360 parents and their child with autism aged 3-12 years old complete all study procedures (180 Treatment, 180 Control).

We will close out the study after enrolling 360 participants with completed endpoints, estimated for 90% power and 2-sided significance of .05 to detect minimal differences in VABS-III Socialization Standard Score of 3.1 points, consistent with the results of a GuessWhat feasibility study previously reported by our lab.

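### Removal for any negative effect depends on volunteered reports, because the first scheduled safety question comes at week 4, when the randomized exposure ends

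*Combined protocol and SAP*

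**What the plan says.** Section 6.3 gives a safety-based rule for ending treatment: "We will remove subjects from treatment if they experience any negative effects". It does not define a negative effect or say how one is detected. Section 4.1 sets the length of exposure: "The intervention period is 4 weeks".

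Section 8.1 first raises safety at the week-4 post-test, where both arms "will be asked about any changes in treatment or safety events at week 4". The text under its week-8 heading also includes a safety check-in, but times it differently: "At week 4 from initial app download date, participants will be asked via email to complete all outcome measures". The week-12 text again refers to week 4. The schedule in section 13 has columns for weeks 0, 1, 4 and 12 and no safety row. The nearest item is the questionnaire on treatment changes and play, marked at weeks 4 and 12.

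Section 7.2 describes the contacts during treatment. Coordinators will "contact participants by phone or email if there is no activity within the first 7 days", and "Participants will receive 3 reminders before being marked as lost to follow-up". The app sends notifications, and "automated email reminders will be sent weekly to remind parents to engage with the app". No safety question is stated for any of these.

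Section 9.3 requires prompt recording of adverse events but gives no method or timing for asking about them. Safety of home use is a secondary objective (section 5.2). The safety population is everyone who receives treatment (section 10.4), not only those who answer at week 4. On retention, section 10.2 says: "We aim to successfully retain 36% of enrolled families".

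**The concern.** A rule that ends treatment needs information while treatment is under way. Here the first planned request for that information coincides with the end of exposure. Until then the rule acts only if a parent reports something unprompted or mentions it in a contact made for compliance.

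The same gap affects the safety objective. If a family stops because the child reacted badly, nothing in the plan asks why it stopped. If that family then does not answer at week 4, it still counts in the safety denominator, and any event is known only if it was volunteered or reported at a later check-in. An event rate built this way cannot separate no event from no question asked.

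**Working it through.** **Step 1: timing.** The contacts between allocation and the end of randomized exposure, with what the plan says each one asks:

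| Contact | Source | When | Safety question stated |
|---|---|---|---|
| App notifications, weekly emails | 7.2, 8.1 | Weeks 1 to 4 | No |
| Coordinator phone call or email | 7.2 | No activity in first 7 days | No |
| Reminders before loss to follow-up | 7.2 | Up to 3, timing not given | No |
| Post-test 1 | 8.1 | Week 4 | Yes, both arms |

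Scheduled safety questions before exposure ends: 0. The coordinator contact is triggered by inactivity in the first 7 days, so as worded it does not clearly cover a family that plays in week 1 and stops later.

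**Step 2: reproduce the plan's retention figure.** Inputs from section 10.2: up to 2,000 participants, 50% enrollment, 36% retention, 360 completers.

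- 2,000 × 0.50 = 1,000 enrolled.
- 1,000 × 0.36 = 360 completers, which matches the plan.
- The alternative reading, 2,000 × 0.36 = 720, does not match, so the first reading is used.

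**Step 3: non-completers at those rates.** 1,000 − 360 = 640, or 64%. With 1:1 allocation and equal non-completion in the arms (an assumption), 640 / 2 = 320 per arm.

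**Step 4: non-completers from the synopsis.** This pairs the minimum enrollment with the minimum number of completers, and the maximum with the maximum.

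- 500 − 360 = 140, and 140 / 500 = 28% (70 per arm).
- 2,000 − 900 = 1,100, and 1,100 / 2,000 = 55% (550 per arm).

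**Step 5: what these figures bound.** Section 10.2 counts families who complete every study procedure. A family can answer at week 4 and miss something else, so each figure is an upper bound, at the stated rates, on missing week-4 safety answers. Only the treatment-arm half bears on randomized exposure, and a treatment-arm family that never plays has not received treatment. At section 10.2's rates, the number of treated families without a week-4 answer is therefore at most about 320. The documents give no week-4 response rate from which to estimate it.

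**The case against.** The strongest case on the other side is proportionality. This is a parent-run game, and section 7.2 reports no critical tasks, no adverse events in testing, and a risk no greater than daily life. A parent starts every session, sees the child's reaction and can stop. The rule works on any report, section 9.3 requires prompt recording, and section 10.5 tabulates related events from any phase. The inactivity contact has no stated script, so a parent could raise a problem there. Consent pages are not among the documents reviewed, so instructions to parents on reporting problems cannot be assumed absent.

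Much of this stands, and it limits the weight of the point. It does not supply a planned question during exposure. Low expected risk is a reason to keep ascertainment light, but the trial has set itself a safety objective.

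A reader might infer four stronger things that the documents do not support:

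- *Families who quit are never asked.* Section 8.1 puts the week-4 question to both arms without limiting it to active users. A family that stops playing but still responds is asked.
- *64% of families give no safety answer.* The 36% is completion of all procedures across both arms.
- *A week-1 event means nine more sessions.* Three weeks at 3 sessions a week is 3 × 3 = 9, but only with full adherence after the event. Feasibility families averaged six days of use over four weeks (section 3.2).
- *This is the only rule for ending treatment.* Section 6.3 also covers suspected fraud.

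**Conclusion.** The point holds as a gap in ascertainment. Section 6.3 sets a rule to be applied during treatment, and the plan schedules no safety question until the 4-week randomized exposure ends. No question is specified when a family stops or before it is marked lost to follow-up.

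The possible loss of solicited week-4 safety data is bounded by non-completion: up to 640 of 1,000 enrolled (about 320 per arm) at section 10.2's rates, or 28% to 55% on the synopsis figures. These bounds rest on the plan's own forecasts and, for the per-arm split, on equal non-completion.

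A reader might go on to conclude that the safety record will look artificially clean. That needs drop-out to be linked to poor tolerability, which is plausible but not shown. What can be said is that events may be learned of late, and that non-response at week 4 cannot be read as absence of events. No efficacy figure or sample size changes. This is a worthwhile, cheap improvement and does not invalidate the design.

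**What to change.** - Add one item to the weekly treatment-arm email asking whether the child has had any negative effect (yes or no, describe), linked to the existing REDCap adverse event form.
- Have the coordinator ask the same item, and the reason for not playing, in the planned inactivity contacts and before a family is marked lost to follow-up. The second point matters for families who stop after the first 7 days.
- If adverse event rates are to be compared between arms, send the same item to controls on the same timetable. Section 8.1 describes weekly reminders only for the treatment arm, so this would be a new automated message.
- Add a safety row to section 13.
- Reconcile sections 6.3, 7.2, 8.1, 9.3 and 13 on how and when negative effects are ascertained, including the week-4 wording under the week-8 and week-12 headings. How the removal rule in 6.3 relates to the severity grades in 9.3 also needs stating. Which events lead to removal is for the sponsor to decide.

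The cost is small but not zero. More minor events will be recorded, and section 9.3 has the principal investigator assess each one. Free text may arrive in three languages, with a single coordinator (section 4.2), and families carry slightly more burden. No endpoint, allocation or sample size changes.

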6.4 Compensation

Following completion of measures after completion of the 4-week intervention period, participants will receive \$50 e-gift card for their participation in the study. Participants who go on to complete T measures will receive a \$20 e-gift card. There will be opportunities for continued follow-up from T3. Participants will be able to volunteer for these additional follow-ups.

7. STUDY TREATMENT - GUESSWHAT

7.1 Study Intervention

We invented a digital treatment, GuessWhat, that operates on smartphones to create a fluid social engagement with an autistic child and his/her social partner to reinforce prosocial learning while simultaneously collecting game metric and video data that can be used to measure the child's progress and symptoms. The GuessWhat app challenges the child to interpret and imitate social and emotion-centric prompts shown on the screen of a smartphone held just above the eyes of a parent/guardian. The parent flips the phone upward/downward if able/unable to correctly guess what the child is acting, switching to the next image in the deck with each flip. The phone's front camera (facing the child) records the entire gameplay session and after each gameplay session, caregivers can choose to share the video with our research team.

Preliminary work to-date resulted in positive user feedback, evidence of engagement for both the parents and children, and meaningful gains in socialization in the child.

Parents and children choose from a variety of different game decks, with decks showing faces emoting the standard Ekman emotion expressions, cartoon characters playing sports activities, occupations, etc. Key mechanisms include facial expression labeling, imitation of varied social emotional prompts, and joint attention with a social partner during play to act out prompts and earn points.

[figure not shown]

Figure 1. Mobile Intervention User Experience. GuessWhat is a mobile game available for any smartphone device that uses varied a) reward systems, and b) social emotional games to help children practice facial expression and emotion recognition, joint attention, and play. In a typical game session, c) the parent and child play a round of “MojiMatch” where the child matches an emoji to an animated GIF of a facial expression. Afterwards, the parent reviews and makes their own choices about the expression. d) Then they play “Act it Out,” where the parent holds the smartphone to their forehead and tries to guess the emotion mimicked by the child in response to the prompt shown on the phone’s screen. Upon guessing, the parent tilts the phone to proceed to the next prompt through the end of the session. After each game, parent and child can review a video of the session together. In-app game modes, unlocking deck and character choices based on coins earned, and activity-based achievement badges reinforce positive progression and ensure optimal child engagement through time.

Standard Dose

GuessWhat is a digital therapeutic application intended to improve socialization skills including joint attention and facial expression/emotion recognition in children with Autism Spectrum Disorder (ASD) between the ages of 3 and 12 years old. It is designed to be used regularly with a **caregiver 3-4 times a week for 15-20 minutes**. GuessWhat is intended for use as a part of a therapeutic program that may include clinician directed therapy, medication, and/or education programs, which further address symptoms of ASD.

